15.2.3. Secondary Analysis

Efficacy/Pharmacodynamic Effects Analysis of Secondary Endpoints:

All efficacy analyses will be performed for the EE and mITT populations.

Efficacy will be evaluated by determining the proportion of patients who have a modified HI-E erythroid response rate based upon the IWG 2006 criteria ([Appendix 5](#)), defined as 1) A mean hemoglobin increase ≥ 1.5 g/dL over an 8-week period as compared to baseline, not influenced by RBC transfusion in NTD patients or 2) A decrease of ≥ 4 units or $\geq 50\%$ of units of RBCs transfused over a period of 8 weeks, relative to the number of units of RBCs transfused in the 8 weeks immediately prior to Cycle 1 Day 1 in TD patients.

Baseline hemoglobin will be the average of two or more measures (not influenced by RBC transfusion) performed during the screening period for study A536-03 (for patients without interruption) or study A536-05 (for patients with interruption).

Baseline units of RBCs transfused will be the 8-week period prior to study A536-03 (for patients without interruption) or study A536-05 (for patients with interruption).

The erythroid response will be summarized using both a point estimate and its exact 95% confidence interval based on binomial distribution.

No direct comparison testing with concurrent or historical controls will be performed.

Analysis of other secondary efficacy/pharmacodynamic endpoints will include:

- Time to HI-E response and duration of HI-E response as per the IWG 2006 criteria and modified IWG criteria.
- Mean RBC transfusion burden
- Rate of RBC transfusion-free period lasting \geq 8 weeks in TD patients.
- Mean hemoglobin level change in NTD patients
- Other PD endpoints including:
 - Biomarkers for iron overload/metabolism
 - Relationship of biomarkers to response
 - Rates of HI-E, HI-N and HI-P

Exploratory endpoints will include:

- Biomarkers related to the TGF β superfamily.
- Patient-reported quality of life using tools including but not limited to the FACT-An questionnaire.

All binary endpoints will be summarized using both a point estimate and its exact confidence interval based on the binomial distribution. The time-to-event type secondary endpoints will be analyzed using Kaplan-Meier method to estimate the survival curve and median time to event and 95% confidence interval.

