## **5.2. General Considerations**

Unless otherwise noted, continuous data will be summarized with the following descriptive statistics: number of observations (n), mean, standard deviation (STD), median, minimum and maximum. Categorical data will be summarized with frequencies (n) and percentages (%). In cases where missing data cause percentages not to sum to 100, a missing data row will be provided. Percentages will use column totals as the denominator unless otherwise indicated. For time to event variables, the Kaplan-Meier curves will be presented if the number of patients is more than 5.

All study data will be included in study data listings. Missing data will generally not be imputed, unless otherwise stated.

Data summaries may also be presented for LTB and HTB patients separately as specified. All summaries will be descriptive. No formal hypothesis testing is planned.

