#### 5.8.2.2. RBC Transfusion Independence

For patients with  $\geq 2$  units of RBC transfusion at baseline, RBC transfusion independence (RBC-TI) response is defined as not requiring RBC transfusion for 8 or more weeks while on treatment.

The proportion of RBC-TI responders will be estimated by a point estimate along with the exact 95% confidence interval based on binomial distribution. The denominator is the number of patients with  $\geq 2$  units of RBC transfusion at baseline.

Time to RBC-TI will be defined as the time from the first dose date to the starting date of the first consecutive 8-week interval not requiring RBC transfusion. Duration of RBC-TI will be calculated as the longest period of time not requiring RBC transfusion during treatment and will be censored at the analysis cutoff date for ongoing responses.

Both time to and duration of RBC-TI will be analyzed as continuous variables and summarized by descriptive statistics for RBC-TI responders only. Duration of RBC-TI will also be analyzed as a time to event variable using Kaplan-Meier method.

The derivations of RBC-TI response, time to and duration of RBC-TI will be listed for each patient.

RBC-TI responders may experience multiple periods of  $\geq 8$  weeks of RBC-TI response. For all RBC-TI responders, the number of episodes and cumulative duration will be summarized. As an exploratory analysis, the cumulative duration of the multiple responses will be analyzed using Kaplan-Meier method.

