#### **5.8.2.5. Time to and Duration of HI-E Response**

Time to and duration of HI-E response will be analyzed for HI-E responders only.

Time to HI-E response will be defined as the time from the first dose date to the first date of any rolling 8-week interval achieving HI-E response.

Duration of HI-E response will be defined as below for LTB and HTB patients, respectively:

- For LTB patients, duration of HI-E response will be calculated as the longest interval during which all hemoglobin measurements have an increase of  $\geq 1.5$  g/dL from baseline.
- For HTB patients, duration of HI-E response will be calculated for the longest such interval as the time from the start date of the first rolling 8-week interval achieving hematologic response to the end date of the last consecutive rolling 8-week interval achieving response.

When there are multiple disjoint intervals with response, the longest interval will be used. Patients with response ongoing by the analysis cutoff day will be censored at that date.

Both time to and duration of HI-E response will be analyzed as continuous variables and summarized by descriptive statistics. In addition, duration of HI-E response will also be analyzed as a time to event endpoint. The survival curves will be estimated using Kaplan-Meier method if the number of patients is more than 5.

HI-E responders may experience multiple periods of  $\geq 8$  weeks of HI-E response. For all HI-E responders, the number of episodes and cumulative duration will be summarized. As an exploratory analysis, the cumulative duration of the multiple responses will be analyzed using Kaplan-Meier method.

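### Durations of RBC-TI and HI-E are also summarised as plain continuous variables, so responses still ongoing at cutoff count as finished and the ordinary mean, and with early censoring the ordinary median, comes out too short

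*SAP*

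**What the plan says.** SAP 5.8.2.2 takes RBC-TI duration as the longest transfusion-free period on treatment, which "will be censored at the analysis cutoff date for ongoing responses". It then plans two treatments of that variable. One is descriptive: "Both time to and duration of RBC-TI will be analyzed as continuous variables and summarized by descriptive statistics for RBC-TI responders only". The other is survival-type: "Duration of RBC-TI will also be analyzed as a time to event variable using Kaplan-Meier method".

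SAP 5.8.2.5 follows the same pattern for HI-E. On censoring: "Patients with response ongoing by the analysis cutoff day will be censored at that date". On the descriptive summary: "Both time to and duration of HI-E response will be analyzed as continuous variables and summarized by descriptive statistics". A time-to-event analysis is added, with a size condition: "The survival curves will be estimated using Kaplan-Meier method if the number of patients is more than 5".

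SAP 5.2 defines the descriptive statistics for continuous data as "number of observations (n), mean, standard deviation (STD), median, minimum and maximum". It has no provision for censored values.

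SAP 5.8 sets each patient's cutoff at the earlier of last dose + 56 days and the last transfusion record.

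Protocol 15.2.3 assigns time-to-event secondary endpoints to the "Kaplan-Meier method to estimate the survival curve and median time to event and 95% confidence interval". It does not mention an ordinary summary of duration. SAP 5.13 does not list that summary as a change.

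**The concern.** A duration that is censored in one sentence and averaged in the next is handled in two incompatible ways. In the averaged version, a patient still responding at cutoff contributes the time observed so far as if the response had ended that day. The result can only equal or fall below the true value, and the shortfall grows with the share of patients still responding. The longer responses last, the more the plain summary understates them.

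Duration of HI-E is a stated secondary objective, and durability is a main reason to run an extension of up to 60 months. A reader of the report could take the ordinary mean or median as the duration of response, or find it beside a longer Kaplan-Meier median with no statement of which one to use.

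**Working it through.** The documents state no duration, responder count or censored share, so there is no plan figure to reproduce. What follows shows direction and possible size. All durations and stopping rates are assumed.

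**Direction.** Let T be the true duration and C the time from response start to the patient's cutoff. The plain summary uses X = min(T, C), and X ≤ T for every patient. The mean of X is therefore below the mean of T as soon as one response is ongoing. The median of X falls below the median of T only if some responses are cut before they reach that median.

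**Closed form.** Take T and C as s plus an exponential, where s = 8 weeks = 56/30.4375 = 1.84 months. Let a = median(T) − s and b = median(C) − s. Then:

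- median(X) = s + ab/(a + b)
- censored share = a/(a + b), before any end-of-treatment cap

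Results in months:

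- Medians of T and C 18 and 60: a = 16.16, b = 58.16. Median(X) = 1.84 + 939.9/74.32 = 14.5. Shortfall 3.5/18, about 19%.
- Medians 18 and 24: a = 16.16, b = 22.16. Median(X) = 1.84 + 358.1/38.32 = 11.2. Shortfall 6.8/18 = 38%.
- Medians 24 and 24: a = b = 22.16. Median(X) = 1.84 + 11.08 = 12.9. Shortfall 11.1/24 = 46%.

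The uncapped censored shares are 16.16/74.32 = 22%, 16.16/38.32 = 42% and 50%. A cap at about 60 months raises them to 25%, 43% and 51% in simulation and leaves these medians unchanged. In simulated samples of 50 responders (3,000 repeats), the Kaplan-Meier median averaged 18.1 and 24.0 months in the second and third cases. The ordinary median averaged 11.3 and 13.0.

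**Second model.** This one follows the plan's timetable more closely:

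- True duration is 56 days plus an exponential.
- Response starts uniformly over days 0 to 84.
- End-of-treatment censoring is at day 1825 + 56 = 1881.
- Stopping while still responding is either absent or has a median of 104 or 52 weeks from response start.
- There are 200,000 simulated responders per row. All times are in weeks.

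| True median | Median time to stopping | Censored | True mean | Ordinary mean | Ordinary median | KM median |
|---|---|---|---|---|---|---|
| 26 | none | 0% | 34 | 34 | 26 | 26 |
| 26 | 104 | 16% | 34 | 30 | 23 | 26 |
| 26 | 52 | 29% | 34 | 26 | 21 | 26 |
| 52 | none | 2% | 72 | 70 | 52 | 52 |
| 52 | 104 | 32% | 71 | 51 | 38 | 52 |
| 52 | 52 | 50% | 72 | 40 | 30 | 52 |
| 104 | none | 16% | 147 | 125 | 104 | 104 |
| 104 | 104 | 51% | 147 | 76 | 56 | 104 |
| 104 | 52 | 69% | 146 | 51 | 38 | 104 |
| 156 | none | 30% | 222 | 157 | 156 | 156 |
| 156 | 104 | 63% | 222 | 88 | 66 | 156 |
| 156 | 52 | 77% | 221 | 57 | 42 | 157 |

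In the four rows with end-of-treatment censoring only, the ordinary median is right and the mean is short wherever anyone is censored. In the eight rows with stopping during response, the ordinary median is short by 3 weeks (26 − 23) to 114 weeks (156 − 42).

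**Which case applies.** The cutoff follows the individual patient's last dose, not a common calendar date. Protocol 9.3 and SAP 3.2 allow treatment to stop for reasons other than loss of response, such as patient request, an adverse event, a WBC rise or sponsor discretion. Stopping while responding, and so early censoring, can occur. How often it does is not stated.

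**Time to response** is summarised in responders only and is fully observed in them, so the point does not reach it.

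**The case against.** The strongest reply is that the right analysis is already there. Both sections plan a time-to-event analysis of duration with ongoing responses censored. All analyses are descriptive, the primary objective is safety, and no test depends on this. That stands, and it limits the point to an extra table.

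A reader might infer more, in four ways that the documents do not support:

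- *That the protocol's Kaplan-Meier median and 95% CI have been dropped.* The SAP sections do not repeat them. But SAP 1 says the SAP is read together with the protocol, and SAP 5.13 does not withdraw them.
- *That small subgroups will be left with the plain figures alone.* SAP 5.8.4 gives no subgroup sizes, and neither document gives responder counts. Only 5.8.2.5 makes estimation of the curves depend on having more than 5 patients. For RBC-TI, 5.2 limits only the presentation of curves, and 5.8.2.2 already lists each patient's duration.
- *That the ordinary median is always too short.* It is not when censoring occurs only at the end of the treatment period.
- *That the report is bound to carry two conflicting medians.* They differ only under early censoring.

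Two modelling objections also have force. The SAP uses the longest of possibly several episodes, whereas the calculations use one per patient. Kaplan-Meier recovers the truth above because censoring was made independent of duration. Treatment may also stop for adverse events, progression or lack of effect, so real censoring may be informative. Observed time in response needs no such assumption, which is a fair reason to allow relabelling as well as deletion.

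**Conclusion.** The point holds as a defect in a duplicate summary. Followed as written, the SAP enters ongoing responses as completed ones for both RBC-TI and HI-E. The resulting mean is too short whenever any response is ongoing at cutoff. The resulting median is too short when responses are censored before the median is reached, which happens if enough patients stop treatment while responding.

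The size cannot be fixed from the documents. The 19% and 38% shortfalls in the median, at 25% and 43% censored, are illustrations that rest on independent exponential censoring and a single episode per patient.

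The Kaplan-Meier analysis is not missing. The one place where the plain figures would be the only summary statistic is HI-E duration with 5 or fewer patients, where 5.8.2.5 plans no curve. The cumulative durations over multiple episodes, also summarised in both sections, share the weakness. The change is worth making because it is cheap and durability matters in an extension study, but no formal conclusion of the trial depends on it.

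**What to change.** In SAP 5.8.2.2 and 5.8.2.5:

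- State that the reported estimate of duration is the Kaplan-Meier median with 95% CI, as in protocol 15.2.3, shown with the numbers of events and censored responses.
- Remove the ordinary mean and median of duration, or relabel them *observed time in response to cutoff* and show the number still ongoing beside them.
- Add a censoring flag to the patient listings. With 5 or fewer HI-E responders, these flagged listings should carry the result.
- Treat the cumulative-duration summaries in the same way.
- Leave the descriptive summary of time to response as it is.
- Note that Kaplan-Meier assumes non-informative censoring at treatment stop, and that this may not hold for every reason for stopping.

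If a relabelled summary is kept, record it in SAP 5.13 as an addition to the protocol. The cost is a few sentences and one table shell, with no new data.

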#### 5.8.2.3. HI-E Response Rate

Erythroid (HI-E) response will be defined following IWG 2006 criteria.

- For low transfusion burden (LTB) patients, a hemoglobin increase of  $\geq 1.5$  g/dL from baseline during any rolling 8-week period in the absence of transfusion. The rolling 8-week period starts and ends at a hemoglobin measurement date with duration  $\geq 8$  weeks.

- For high transfusion burden (HTB) patients, a reduction by  $\geq 4$  RBC units transfused during any rolling 8-week interval on treatment compared to baseline.

A point estimate of the proportion of HI-E responders will be presented along with its associated exact 95% confidence interval based on binomial distribution. HI-E response will also be listed for each patient.

There are two versions of a HI-E response for LTB patients.

- All hemoglobin values increase of  $\geq 1.5$  g/dL from baseline during any rolling 8-week period in the absence of transfusion.
- Mean hemoglobin value increase of  $\geq 1.5$  g/dL from baseline during any rolling 8-week period in the absence of transfusion.

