10.2.2. RBC Transfusions

Concurrent treatment for anemia with blood transfusions is allowed, at the discretion of the investigator, for low hemoglobin levels, symptoms associated with anemia (e.g., hemodynamic or pulmonary compromise requiring treatment) or comorbidity.

For any RBC transfusions (NTD or TD patients) received during the study, collect hemoglobin values just prior to transfusion.

Each TD patient will have a “pre-transfusion hemoglobin threshold” for requiring transfusion, which will be calculated based on transfusion history and will be used for determining when to transfuse during the study. The baseline pre-transfusion hemoglobin threshold will be the mean of all documented pre-transfusion hemoglobin values during the 12 weeks prior to C1D1 of base study A536-03 for patients without treatment interruption, or prior to C1D1 of study A536-05 for patients with treatment interruption. During treatment, if the pre-transfusion hemoglobin level is increased by ≥ 1 g/dL compared to the baseline pre-transfusion hemoglobin threshold for that patient, transfusion should be delayed by a minimum of 7 days and/or the number of units transfused should be reduced by 1 or more RBC units. Patients should not be transfused if hemoglobin is ≥ 9 g/dL unless indicated for symptoms related to anemia or other reasons at the investigator’s discretion.

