24.5. Appendix 5: International Working Group (IWG) Criteria - Erythroid Response Evaluation¹

Hematologic Improvement (HI) ^a	Response Criteria (Responses must last at least 8 weeks)
Erythroid response (Hi-E) (pretreatment Hgb < 11 g/dL)	Hgb increase of ≥ 1.5 g/dL for patients not transfused; or, as defined by having received less than 4 units of RBCs within 8 weeks of Cycle 1 Day 1 Reduction by ≥ 4 units of RBCs transfused (for a Hgb ≤ 9.0 g/dL) during any 8-week period on study, compared with the 8-week period prior to study day 1
Platelet response (HI-P) (pretreatment, $< 100 \times 10^9/L$)	Absolute increase of $\geq 30 \times 10^9/L$ for patients starting with $> 20 \times 10^9/L$ platelets Increase from $< 20 \times 10^9/L$ to $> 20 \times 10^9/L$ and by at least 100%
Neutrophil response (HI-N) (pretreatment, $< 1.0 \times 10^9/L$)	At least 100% increase and an absolute increase $> 0.5 \times 10^9/L$

^a Pre-treatment counts are averages of at least 2 measurements (not influenced by transfusions) ≥ 1 week apart within 28 days prior to Day 1.

Hgb: indicates hemoglobin; RBC: red blood cell; HI: hematologic improvement.

24.6. Appendix 6: National Cancer Institute (NCI) Common Terminology Criteria for Adverse Events (CTCAE) Version 4.0

See <http://evs.nci.nih.gov/ftp1/CTCAE/CTCAE>

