#### Baseline

For patients who roll over to Study A536-05 without interruption, the baseline for Study A536-03 will be used as the baseline for Study A536-05.

For patients who enter Study A536-05 with interruption, the last value on or before the first dose of Study A536-05 will be considered as the baseline unless otherwise specified. For baseline assessments that are not scheduled in A536-05 study or data collection is inadequate at the baseline of Study A536-05, the baseline value for Study A536-03 will be used as the baseline for Study A536-05.

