**Baseline Transfusion Burden**

Baseline transfusion burden will be calculated as the total amount of RBC transfusion during the 8 weeks prior to Cycle 1 Day 1.

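### SAP 5.8.2.3 counts every red-cell unit in the HTB HI-E response, an undeclared departure from Appendix 5's hemoglobin ≤ 9.0 g/dL condition, so a change in transfusion practice can be scored as response

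*SAP*

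**What the plan says.** - **Protocol Appendix 5 (24.5)** defines HI-E in transfused patients as "Reduction by ≥ 4 units of RBCs transfused (for a Hgb ≤ 9.0 g/dL) during any 8-week period on study", compared with the 8 weeks before study day 1.
- **SAP 5.8.2.3** states "Erythroid (HI-E) response will be defined following IWG 2006 criteria". Its HTB bullet then asks for a reduction of at least 4 "RBC units transfused during any rolling 8-week interval on treatment compared to baseline", with no hemoglobin condition.
- **SAP 5.1** does not filter the comparator either: "Baseline transfusion burden will be calculated as the total amount of RBC transfusion during the 8 weeks prior to Cycle 1 Day 1". For patients who rolled over without interruption, "the baseline for Study A536-03 will be used as the baseline for Study A536-05".
- **Protocol 10.2.2** says "Patients should not be transfused if hemoglobin is ≥ 9 g/dL unless indicated for symptoms related to anemia", or for other reasons at the investigator's discretion. It also asks for a delay of at least 7 days and/or at least one unit fewer when pre-transfusion hemoglobin is 1 g/dL or more above the patient's threshold. These rules are framed as applying during the study and during treatment.
- **Protocol 10.2.2** further requires, for any transfusion "received during the study, collect hemoglobin values just prior to transfusion". The threshold itself uses documented pre-transfusion values from the 12 weeks before Cycle 1 Day 1.
- **SAP 5.13** lists five changes from the protocol. Dropping the hemoglobin condition is not among them, although protocol 15.5 says that deviations from its analyses will be indicated in the SAP.

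**The concern.** There are two problems. The first is labelling: the HTB rate would be reported as IWG 2006 HI-E while omitting a condition that the protocol's own statement of those criteria contains.

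The second is comparability. The baseline 8 weeks lie before Cycle 1 Day 1 (of A536-03 for rollover patients), and no section of these documents applies the 9 g/dL rule to them. If a site transfused above 9 g/dL before the study, some baseline units are of a kind that the on-study rule discourages. When they stop, the all-units count falls even if the drug does nothing, and there is no control arm in which the same fall would show. HI-E also feeds time to and duration of response (SAP 5.8.2.5) and the logistic regressions (SAP 5.8.4).

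**Working it through.** The plan gives no expected HI-E rate, power or sample-size calculation, so there is no figure of its own to reproduce.

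**Step 1. Unit arithmetic.** Assume no drug effect, and that the on-study rule removes exactly the units given above 9 g/dL. Let b be the baseline units in 8 weeks and k the number given above 9. On-study units are then b − k. The SAP reduction is b − (b − k) = k. Counting only units at ≤ 9.0 in both periods, the reduction is (b − k) − (b − k) = 0.

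| b | k | On study | SAP reduction | SAP HI-E | Reduction, ≤ 9.0 units only |
|---|---|---|---|---|---|
| 8 | 4 | 4 | 4 | yes | 0 |
| 6 | 4 | 2 | 4 | yes | 0 |
| 8 | 3 | 5 | 3 | no | 0 |
| 8 | 0 | 8 | 0 | no | 0 |

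A patient thus needs at least 4 baseline units above 9 g/dL to become a responder by this route alone.

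**Step 2. How often k reaches 4.** Let q be the share of baseline units given above 9 g/dL. The documents do not give q, so it is an assumption. Treating units as independent (a simplification), the probability is P(X ≥ 4) with X ~ Binomial(b, q).

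| b | q = 0 | 0.1 | 0.2 | 0.3 | 0.5 |
|---|---|---|---|---|---|
| 4 | 0 | 0.0001 | 0.002 | 0.008 | 0.063 |
| 6 | 0 | 0.001 | 0.017 | 0.071 | 0.344 |
| 8 | 0 | 0.005 | 0.056 | 0.194 | 0.637 |
| 10 | 0 | 0.013 | 0.121 | 0.350 | 0.828 |

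The effect is nil at q = 0 and large only when burden and q are both high.

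**Step 3. Simulation under the SAP's window.** All inputs are assumptions: 20,000 patients per scenario, hemoglobin falling 0.45 to 1.0 g/dL per week, weekly SD 0.3, and 2 units given below the trigger, each adding 0.9 g/dL. Baseline is restricted to at least 4 units, the on-study trigger is the lower of the site's trigger and 9.0, and there is no drug effect. The table gives the percentage reaching a reduction of at least 4 units, all units counted.

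| Prior trigger (g/dL) | First 8 weeks only | Any 8-week window in 52 weeks | Added to trigger 9.0 (any window) |
|---|---|---|---|
| 9.0 | 5.5 | 28 | – |
| 9.5 | 10 | 29 | 1 |
| 10.0 | 17 | 32 | 4 |
| 10.5 | 25 | 35 | 7 |

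Here the SD is week-to-week variation that carries forward. If it is treated as measurement scatter that does not carry forward, the any-window rates are 7.5, 9, 14 and 21%, so the additions are 1.5, 6.5 and 13.5 points. Levels depend on modelling details. The gradient does not.

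**Step 4. What the restricted count does.** In the first version of the model, only about 36%, 2% and 0% of HTB patients at triggers 9.5, 10.0 and 10.5 keep 4 qualifying baseline units. With a drug effect that fully stops the hemoglobin decline, at trigger 9.5 the first-8-week response rate is 97% counting all units and about 34% counting qualifying units over all HTB patients. Among those who can respond it is 34/36 ≈ 94%. The denominator therefore has to be stated.

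**The case against.** **The SAP could be read as importing the condition.** It says that it follows IWG 2006. But a programmer will code the explicit bullet and the baseline definition, and neither carries a hemoglobin limit.

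**Applying the condition to baseline is an interpretation.** In Appendix 5 the parenthesis directly qualifies the on-study units, and the comparison clause does not repeat it. This is fair. Yet filtering only the on-study period would compare restricted units with unrestricted ones and inflate reductions further, so the like-for-like reading is the workable one.

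**The mechanism may not operate.** The 9 g/dL rule allows exceptions for symptoms and discretion, and no section says that any site transfused above 9 g/dL. For interrupted patients the baseline may overlap screening or A536-03 follow-up, and the full A536-03 transfusion rules are not in these documents. All of this stands: the claim is that a practice change can be scored as response, not that it is.

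**Most false response in the model comes from elsewhere.** At a prior trigger of 9.0 the any-window rate is already 28%, because any one of many windows suffices. This stands too. It is a separate matter that this fix does not address.

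**A shift in practice would be visible.** SAP 5.8.2.1 lists all hemoglobin and transfusion records, and 5.8.2.10 summarizes change in pre-transfusion hemoglobin in HTB patients. That helps a reader notice a shift but does not correct the rate.

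**Conclusion.** The departure from Appendix 5 is certain and undeclared, and the resulting rate would be mislabelled. The bias it allows is possible but of unknown size. It is zero if no baseline units were given above 9 g/dL. Under the any-window rule it is about 1 to 7 percentage points at prior triggers of 9.5 to 10.5 g/dL (1.5 to 13.5 with measurement-type noise). These figures rest on the assumed hemoglobin decline, SD and unit increment, and on full adherence to the 9 g/dL rule. Severity is moderate: the primary objective is safety, HI-E is secondary and descriptive, and no error rate or sample size is affected.

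A reader might infer three stronger things that the documents do not support:

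- **That false response rises from about 5% to 25%.** This holds only for the first 8 weeks of treatment, whereas the SAP scores any rolling window.
- **That the restricted count nearly eliminates false response at little cost.** In the model its false rate in the first 8 weeks is 0.2% or less at triggers of 9.5 and above, but largely because few patients there keep the 4 units needed to respond at all.
- **That the modified HI-E is also a deviation.** Protocol 8.2 and 15.2.3 and SAP 5.8.2.1 agree on it, with no hemoglobin condition. It shares the exposure (4 baseline units with 2 above 9 leave 2, a 50% fall), but the SAP follows the protocol.

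**What to change.** - **SAP 5.8.2.3:** for HTB patients, count only units with pre-transfusion hemoglobin ≤ 9.0 g/dL, in the baseline 8 weeks and in each on-treatment window.
- **Missing values:** state one rule for units with no pre-transfusion value, for example counting them in both periods.
- **Denominator:** give the rate among HTB patients with at least 4 qualifying baseline units, with the number excluded.
- **Side by side:** report the all-units rate next to it, labelled as not applying the IWG 2006 / Appendix 5 hemoglobin condition. Say which version feeds 5.8.2.5 and 5.8.4.
- **SAP 5.13:** declare the handling.
- **Modified HI-E:** leave the definition unchanged. A sensitivity analysis with the restricted count is optional.

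The cost is SAP text and programming. On-study pre-transfusion values are already collected, and documented values from the 12 weeks before Cycle 1 Day 1 cover the 8-week baseline. The transfusion rules are not in question.

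The downside is that some baseline values may be missing and the Appendix 5 denominator may be materially smaller, not just the rate slightly lower. Two small effects also remain. A unit given at exactly 9.0 g/dL qualifies yet falls under the on-study restriction, and the delay-or-fewer-units rule also acts below 9 g/dL.
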